14.7.3. Handling of Missing Data

Measurements with unknown values or unavailable estimates will be treated as missing values and excluded from the analysis. No imputation of missing data will be performed.

15. ETHICS & REGULATORY CONSIDERATIONS

The study will be conducted in compliance with the principles of the Declaration of Helsinki (1996), the principles of GCP and in accordance with all applicable regulatory requirements including but not limited to the Code of Federal Regulations and FDA guidance documents.

This protocol and related documents will be submitted for review to all relevant IRBs or EC delegated to approve the study at their respective sites. Any amendment to the protocol may be proposed by the principal investigator. The amendment must be submitted to the relevant IRB or EC. When applicable, the implementation of the amendment will take place only once approved by the appropriate ethics committee.

Annual progress and safety reports and a final report at conclusion of the study will be submitted by Exalenz Bioscience (or on behalf of the Sponsor), to the FDA and the IRB/EC within the timelines defined in the Regulations.

Exalenz Bioscience Ltd.	Last update on: Mar. 12, 2017
Study Title: Clinical Study to Confirm Safety and Accuracy in Detection of H. pylori with ¹³C-Urea Breath Test using the BreathID® Hp and BreathID® Hp Lab Systems in the Pediatric Population	Protocol Number: PED-HP-0616B Version 2.0
Document No.: CSD00092	Page 48 of 59

16. INVESTIGATOR RESPONSIBILITIES

The investigator is responsible for ensuring that the clinical study is performed in accordance with the protocol, current ICH guidelines on GCP, US-GCP and applicable regulatory requirements. GCP is an international ethical and scientific quality standard for designing, conducting, recording, and reporting studies that involve the participation of human subjects. Compliance with this standard provides public assurance that the rights, safety, and well-being of study subjects are protected, consistent with the principles that originated in the Declaration of Helsinki, and that the clinical study data are credible.

The investigational devices and substrate accountability will be filed in the Investigator's Study File. Study supplies logged in will be kept by the investigator or the delegated persons in a secure place. All supplies (device, substrate / kits) will be used for this study only. After completion of the study, the device, kits and all unused accessories must be returned to Exalenz Bioscience Ltd. as per their request or alternatively, destroyed according to local regulations after receiving explicit authorization by Exalenz to do so and provide Exalenz with a confirmation.

The Principal Investigator will act as custodian for the study data. Subject data will be pseudonymized and it will be stored on password protected media. All data will be compliant with CFR and GCP.

17. SAFETY CONSIDERATIONS

17.1. *Adverse Event Definitions*

An adverse event (AE) is any undesirable or unintentional event that occurs in a patient or clinical investigation subject, whether or not considered related to the investigational product; this includes clinically significant changes in laboratory values. As this study is not therapeutic in nature, there will be no therapeutic failures to report.

Regardless of severity or relationship to the study investigational product, all diagnoses, symptom(s), sign(s) or finding(s) with a start date after the first study test has begun (Breath test/stool test) and until the last study procedure is being completed will be documented, assessed by the investigator and recorded in the subject's CRF. A surgical procedure that was planned prior to the first study test by any physician treating the subject should not be recorded as an AE.

Exalenz Bioscience Ltd.	Last update on: Mar. 12, 2017
Study Title: Clinical Study to Confirm Safety and Accuracy in Detection of H. pylori with ¹³C-Urea Breath Test using the BreathID® Hp and BreathID® Hp Lab Systems in the Pediatric Population	Protocol Number: PED-HP-0616B Version 2.0
Document No.: CSD00092	Page 49 of 59

17.2. Serious Adverse Event (SAE), Unanticipated Adverse Device Effect (UADE) and Suspected Unexpected Serious Adverse Reactions (SUSAR)

A serious adverse event (SAE) is an event that is either:

- a) Fatal
- b) Life-threatening

Life threatening is defined as an event in which the patient is at risk of death at the time of the event. It does not refer to an event that hypothetically might have caused death if it was more severe.

- c) Results in persistent or significant disability/incapacity

Disability is defined as a substantial disruption of a person's ability to conduct normal life functions.

- d) Requires or prolongs inpatient hospitalization
- e) A congenital anomaly or birth defect.
- f) Another serious or important medical event as judged by the investigator.

An Unanticipated Adverse Device Effect (UADE) or a Suspected Unexpected Serious Adverse Reactions (SUSAR) is an SAE, related to the investigational product, for which the nature or severity is not consistent with the expected outcomes of the treatment/testing being offered.

An unexpected adverse event is one that has not been previously observed, or one that is of a specificity or severity not consistent with the current investigator brochure.

As with every procedure risks and discomforts may occur with relations to the Breath ID test. The potential risks/complications and discomforts which may be associated with all study procedures are listed below.

- Allergic and/or other reactions to BreathID reagent
- Aspiration (inhaling) of food or fluids into the lungs
- Discomfort

Exalenz Bioscience Ltd.	Last update on: Mar. 12, 2017
Study Title: Clinical Study to Confirm Safety and Accuracy in Detection of H. pylori with ¹³C-Urea Breath Test using the BreathID® Hp and BreathID® Hp Lab Systems in the Pediatric Population	Protocol Number: PED-HP-0616B Version 2.0
Document No.: CSD00092	Page 50 of 59

When an adverse event occurs, the following information and assessments should be documented in the subject's file and reported in the adverse event section of the CRF:

- The signs, symptoms, or diagnosis of the event if available
- The date and time of onset of the event using the 24 hour clock where midnight is 00:00 and noon is 12:00
- The adverse event severity using the criteria outlined below
- The relationship of the event to the study medical device or drug as outlined below
- Describe any action taken regarding study medical device or drug disposition
- List any required therapy, medication, treatment, or diagnostic procedure.

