Although it is believed that the efficacy of the test can be fully extrapolated from the adult data, subject's *H. pylori* status will also be collected as part of this study in order to further support and confirm the efficacy of the breath test in the pediatric population.

The safety of the specific drug substance in children at the dose utilized in the test setting remains to be established in this study. The dose has been proven to be both safe and effective in adults in clinical trials as well as in routine clinical use in more than 150,000 subjects.

Upper endoscopy - Esophagogastroduodenoscopy (EGD) is generally not standard of care for evaluation of children with symptoms associated with *H. pylori* infection. As such, it is difficult to justify performing the procedure which requires sedation only for the research purpose. Children are evaluated for *H. pylori* infection most commonly with stool antigen

Exalenz Bioscience Ltd.	Last update on: Mar. 12, 2017
Study Title: Clinical Study to Confirm Safety and Accuracy in Detection of H. pylori with ¹³C-Urea Breath Test using the BreathID® Hp and BreathID® Hp Lab Systems in the Pediatric Population	Protocol Number: PED-HP-0616B Version 2.0
Document No.: CSD00092	Page 10 of 59

testing. Therefore, this study proposes to test the drug and its dosing in symptomatic children suspected of having *H. pylori* who will undergo both a breath test and an FDA cleared stool test. The stool test has a sensitivity and specificity ranging from 90 to 97%, and comparing the breath test to the stool test results will confirm that the use of this test is reasonable in the target population.

This study will enroll all-comers whether for initial diagnosis or post-eradication testing. It will predominantly (approximately 2/3) enroll children under the age of 12 to confirm drug/dose tolerance and confirm its efficacy. Older children between 12 and 18 years are similar to adults and no more than a third (approximately 1/3) will be enrolled from this age group.

Description of Test:

The ¹³C-Urea Breath Test is performed using a test kit that contains 75mg of non-radioactive ¹³C-urea and citric acid to be dissolved in tap water ("solution").

Exhaled breath will be collected using:

- (1) a nasal cannula for continual passive collection of breath samples from the nose before and after ingestion of the solution, and/or

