11. STUDY OBJECTIVES

This study is primarily designed to confirm tolerance of the dose used for the pediatric population. The ¹³C-urea and citric acid (NDA-21-314) are contained in **IDkit:Hp™ One** in the **BreathID® Hp System** (K130524) and **IDkit:Hp™ Two** in the **BreathID® Hp Lab System** (K162150). Additionally the efficacy of the respective means of breath collection, the nasal cannula contained in **IDkit:Hp™ One** and breath collection bags contained in **IDkit:Hp™ Two**, will be confirmed to be similar in the pediatric population as that of adults.

Three studies were published using the BreathID device with nasal cannula and 75mg ¹³C-urea in over 100 pediatric subjects^(2, 10, 11). As such, the UBT with the data obtained for adults can be extrapolated for pediatrics (as confirmed with FDA through Q170072) and a confirmatory trial is deemed sufficient.

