12. SUBJECT SELECTION

Consecutive pediatric subjects aged between 3 and 18 years of age evaluated by the physician, or presented by referral from other institutions or physicians who are clinically indicated to undergo *H. pylori* testing and meet study criteria will be enrolled. Distribution of subject's ages will be monitored to assure all age ranges are represented. To confirm safety and performance of the tests in younger children, this study will predominantly (approximately 2/3) enroll children under the age of 12 to confirm drug/dose tolerance and safety and confirm its efficacy.

Consent to participate in the study and to undergo the breath test procedures must be obtained from the legal representative/guardian of every subject following a thorough explanation of the study, including the benefits and risks (if any). The majority (approximately 2/3) of the subjects will be from US centers. Assent will also be obtained from those subjects above the age that local regulations require consenting of the child.

All subjects screened will be documented in a screening log, regardless of subsequent entry into the study. Reasons for non-inclusion will be recorded.

12.1. *Inclusion Criteria*

To be eligible to participate in this study, subjects must meet all of the following inclusion criteria:

- Be older than 3 and younger than 18 years of age
- Present with clinical indication compatible with *H. pylori* based on the judgement of the treating physician (such as abdominal pain, nausea, diarrhea, reflux, peptic ulcer, dyspepsia, etc., or following treatment for *H. pylori*)
- Subject/Legal guardian (and subject when relevant) is willing to sign the Informed Consent/Assent Form

Exalenz Bioscience Ltd.	Last update on: Mar. 12, 2017
Study Title: Clinical Study to Confirm Safety and Accuracy in Detection of H. pylori with ¹³C-Urea Breath Test using the BreathID® Hp and BreathID® Hp Lab Systems in the Pediatric Population	Protocol Number: PED-HP-0616B Version 2.0
Document No.: CSD00092	Page 37 of 59

- Naïve to *H. pylori* treatment in the past 6 weeks

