13. STUDY ASSESSMENTS AND PROCEDURES

13.1. Study Visits

The clinical study will be conducted in compliance with this protocol and in accordance with the ethical principles under Investigational Review Board (IRB) or Helsinki committee approval consistent with Good Clinical Practice (GCP) and with the applicable local regulatory requirements.

The investigator(s) at each site will sign a Protocol Approval Page (**Appendix A**).

Screening and Baseline can be performed at the same visit

Exalenz Bioscience Ltd.	Last update on: Mar. 12, 2017
Study Title: Clinical Study to Confirm Safety and Accuracy in Detection of H. pylori with ¹³C-Urea Breath Test using the BreathID® Hp and BreathID® Hp Lab Systems in the Pediatric Population	Protocol Number: PED-HP-0616B Version 2.0
Document No.: CSD00092	Page 39 of 59

13.1.1. Screening Visit (can be done up to 37 days prior to the breath test)

1. The legal guardian (and subject if applicable) will sign the consent/assent form prior to performing any study related procedures. The child will sign the assent form if, based on his age, local regulations require the child to sign the form.
2. The investigator(s), co-investigator(s) or study coordinator will record:
 - Demographic information.
 - Medical history including information regarding H. pylori results.
 - Concomitant medications (starting 6 weeks prior to the planned breath test/stool test)

This will be performed for each subject in order to establish compliance with the inclusion and exclusion criteria.

13.1.2. Baseline Visit Day 1

1. The investigator(s), co-investigator(s) or study coordinator will record any changes from screening visit in medical history including changes in concomitant medications (starting 6 weeks prior to the breath test/stool test) for each subject to establish compliance with the inclusion and exclusion criteria.
2. Physical examination including height and weight of the subject will be performed.
3. A urine pregnancy test will be performed for females of childbearing potential who did not have a pregnancy test within 7 days prior to the breath test.
4. Inclusion and exclusion criteria will be checked.

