14. STATISTICAL CONSIDERATIONS

14.1. *Study Design and Objectives*

The study is designed as multi-center, open label study, designed to confirm the safety and the efficacy of ¹³C-urea breath test using the **BreathID® Hp and BreathID® Hp Lab Systems** in pediatric subjects and confirm the efficacy of the respective means of breath collection, the nasal cannula and breath collection bags, in this population compared to *stool antigen* testing. A central lab will analyze the stool specimens. Children, that cannot inflate the breath collection bags, may perform UBT only with **IDkit:Hp One** nasal cannula. All children will be exposed to non-radioactive ¹³C-urea and citric acid. Subjects will be enrolled on a walk-in basis. Subjects will be treated only based on the established methods

Exalenz Bioscience Ltd.	Last update on: Mar. 12, 2017
Study Title: Clinical Study to Confirm Safety and Accuracy in Detection of H. pylori with ¹³C-Urea Breath Test using the BreathID® Hp and BreathID® Hp Lab Systems in the Pediatric Population	Protocol Number: PED-HP-0616B Version 2.0
Document No.: CSD00092	Page 44 of 59

used in the local routine clinical practice and the investigator and treating physician will remain blinded to the breath test results until the end of the study.

14.2. *Endpoints*

14.2.1. *Primary Endpoint: Safety*

Adverse event rate: The safety of the ¹³C-urea/citric acid solution has been previously established in adults and in children in literature⁽¹⁻³⁾. Any adverse event (whether related or not) will be recorded. There are no safety concerns and no adverse events anticipated for the breath tests.

14.2.2. *Secondary Endpoints: Efficacy*

1. Overall agreement in diagnosis (presence/absence of *H. pylori*) between the **BreathID® Hp System** results where breath is collected using **IDkit:Hp™ One** via a nasal cannula applying the 5 DOB threshold in pediatric subjects and stool antigen outcome or biopsy results in the pediatric population.
2. Overall agreement in diagnosis (presence/absence of *H. pylori*) between the **BreathID® Hp Lab System** results when analyzing **IDkit:Hp™ Two** breath sample bags using the 5 DOB threshold in pediatric subjects and the stool antigen outcome or biopsy results in the pediatric population.

14.2.3. *Study Hypotheses*

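### Section 17.1 does not say that post-test worsening of a symptom already present at entry is an adverse event, and its start-date rule can be read to leave it out of the primary adverse event rate

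*Combined protocol and SAP*

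**What the plan says.** Section 11 gives the purpose: "This study is primarily designed to confirm tolerance of the dose used for the pediatric population". Section 14.2.1 makes the adverse event rate the primary endpoint and adds "Any adverse event (whether related or not) will be recorded".

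Section 17.1 has two relevant sentences. The definition is broad: "An adverse event (AE) is any undesirable or unintentional event that occurs in a patient or clinical investigation subject", whether or not it is considered related. The recording instruction that follows covers "all diagnoses, symptom(s), sign(s) or finding(s) with a start date after the first study test has begun", through completion of the last study procedure, where the first test may be the breath test or the stool test. Sections 17.1 to 17.5 neither include nor exclude an increase in severity or frequency of a symptom that was already present.

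Section 12.1 requires a clinical indication, "such as abdominal pain, nausea, diarrhea, reflux, peptic ulcer, dyspepsia, etc", or a history of *H. pylori* treatment. The synopsis confirms the second route: "This study will enroll all-comers whether for initial diagnosis or post-eradication testing".

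Before the drink, Section 13.1.1 collects "Medical history including information regarding H. pylori results". Section 13.1.2 updates history and medications and adds a physical examination. Neither these lists nor the schedule table asks for a severity grade of presenting symptoms.

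**The concern.** The study is mainly about tolerance of an oral drink, and many of its subjects come because of upper or lower gastrointestinal symptoms. A child with weeks of nausea has a symptom whose start date precedes the first test. If that nausea becomes clearly worse minutes after the drink, a coordinator who follows the recording sentence literally need not enter it. Another coordinator, relying on the definition, would enter it. The synopsis allows up to 8 US sites and possibly others abroad, so the primary count could depend on which sentence each site follows.

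Differences of this kind do not cancel. Omitting a worsening can only lower the reported rate, and the children whose worsening could be missed are those with symptoms at entry.

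**Working it through.** **Step 1. Set the sentences side by side.** Take a symptom present at entry that worsens after the drink.

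- By the Section 17.1 definition, the worsening can be an undesirable event and so an adverse event.
- By the Section 17.1 recording rule, the symptom's start date precedes the first test, so a literal reading does not call for it.
- Section 17.2 asks for the date and time of onset of the event. If the worsening is treated as the event, its onset is after the test and it is recorded. If the symptom is treated as the event, it is not.

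The plan does not choose between these readings. Timing adds an anomaly. Section 13.1.3 allows the stool test up to 7 days before the breath test. A symptom that starts between the two, before any drink, falls inside the window, while a worsening straight after the drink may fall outside it.

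**Step 2. Reproduce the plan's safety figure.** Section 14.3 states that 35 evaluable subjects with no related serious events give an upper two-sided 95% limit of at most 10%. For 0 events the exact (Clopper-Pearson) upper limit is 1 − 0.025^(1/n).

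- n = 35: 1 − 0.025^(1/35) = 10.0% (10.003% before rounding).
- n = 40, the planned minimum: 1 − 0.025^(1/40) = 8.8%.

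The figure reproduces to rounding. It concerns related serious events, not the adverse event rate, so 10% serves here only as a reference for scale.

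**Step 3. Illustrate the effect of an omission.** The documents give no rate of worsening, so the counts below are assumed. Exact two-sided 95% limits at n = 40:

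| Events counted | Rate | 95% limits |
|---|---|---|
| 0 | 0% | 0 to 8.8% |
| 1 | 2.5% | 0.06% to 13.2% |
| 2 | 5.0% | 0.6% to 16.9% |
| 3 | 7.5% | 1.6% to 20.4% |

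The difference between the first row and a later row is what that many unrecorded worsenings would hide if nothing else were recorded. One is enough to move the upper limit from 8.8% to 13.2%.

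**Step 4. Apply the relatedness step.** Section 14.7.1 Safety Analysis attaches the exact interval to events related to drug or device; all adverse events get incidence tables. Section 17.3 classes an event as not related when it is clearly due to the child's clinical state or has a highly likely alternative explanation. A recorded worsening would therefore always appear in the tables, but would enter the interval only if judged related. That judgement is harder without a grade of the same symptom taken before the drink.

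**The case against.** The strongest reply is that silence is not exclusion. The definition in 17.1 is wide enough for a worsening, and the only thing the section says should not be recorded is a surgical procedure planned beforehand. Section 17.2 lists reactions to the reagent and discomfort among the risks, so a reaction to the drink could be entered under either, whatever the child's history. All of this stands. A reader might infer that 17.1 removes worsening from the endpoint; the documents do not support that. They leave it open.

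Three other inferences also go too far.

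- That the drink is known to provoke the presenting symptoms. The plan does not say so. It names allergic or other reactions, aspiration and discomfort, and otherwise refers to labels that are not reproduced.
- That every child is symptomatic. Post-eradication entrants need not be.
- That worsening could never be reconstructed. Medical history, the physical examination and source records may hold symptom detail, and the eCRF is not shown. What can be said is that the protocol does not require a severity grade before the drink.

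It is also fair to object that, without a control group, counting worsening will pick up natural fluctuation. That is a real cost, and it is a reason to grade symptoms beforehand so that relatedness can be judged.

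None of this removes the ambiguity. Two sentences in one section point different ways on events that bear on the primary endpoint.

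**Conclusion.** The point holds as an ambiguity that can understate the primary adverse event rate. Section 17.1 selects events by start date, does not mention worsening, and is applied to a population in which many children have gastrointestinal symptoms at entry. Under-recording is possible, not certain, and depends on how each site reads the section.

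The size cannot be estimated from the documents. With an assumed single missed event and no others, 0/40 (upper limit 8.8%) would have been 1/40 (2.5%, 0.06% to 13.2%). This assumes that the worsening is not recorded at all; for the interval under Safety Analysis it also assumes that the event would have been judged related. The illustration shows how sensitive a 40-subject rate is to one event. It does not forecast how many will be missed.

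**What to change.** In Section 17.1, replace the start-date rule with one that covers any sign, symptom or diagnosis that starts, or increases in severity or frequency, after the first study test begins. State that for a symptom already present, onset is the date and time of worsening.

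In Section 13.1.2 and the schedule table, add a record, taken at the Baseline visit before the drink, of each presenting gastrointestinal symptom: present or absent and, if present, its severity on the mild/moderate/severe scale of Section 17.4. This gives the investigator a reference for judging both worsening and relatedness.

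The cost is a sentence in 17.1 and a short item on the Day 1 eCRF page, with no added visit. The reported rate may be somewhat higher and, with no control group, will include some natural fluctuation of symptoms; the report should say so. Asking about each symptom at every adverse event assessment is optional and not needed for this fix.
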